10.1.4 Missing Data Imputations

Missing data will be imputed using the following methods for the efficacy analyses:

- Non-Responder Imputation (NRI): The NRI analysis will categorize any subject who has missing value at a specific visit as non-responder for that visit. The only exception is when if the subject is a responder both before and after this specific visit window, then the subject will be categorized as a responder for the visit. The NRI will be the primary approach in the analysis of categorical variables. Of note, this before- and after-window imputation will utilize visits across Part A and B for the risankizumab arms.
- Last Observation Carried Forward (LOCF): The LOCF analyses will use the completed evaluation from the previous visit for efficacy measures assessed to impute missing data at later visits. For observations in RZB_75/RZB_75, and RZB_150/RZB_150 arms in Part B, LOCF is continued across Part A and Part B. LOCF will be applied to the observations in PBO/RZB_75, and PBO/RZB_150 arms within the analysis period. Baseline values will not be carried forward. LOCF will be the primary approach in the analyses of continuous variables, and the secondary approach in the analyses of categorical variables.
- As-observed: The as-observed analysis will not impute values for missing evaluations, and thus a subject who does not have an evaluation on a scheduled visit will be excluded from the as observed analysis for that visit. As-observed analysis will be the secondary approach in the analysis of continuous variables.
- Multiple Imputation (MI): The MI will be used as sensitivity approach to impute missing data in primary endpoints. The variables to be included in the imputation model are listed below. If MI is not applicable due to the nature of our data (e.g., MCMC algorithm does not converge), logistic regression or mixed effect model repeat measurement (MMRM) methods will be applied as sensitivity approach, whichever applicable.

The Multiple Imputation analysis will be carried out in three steps.

- Imputation of missing data. The imputation will be generated for each efficacy endpoint measurement. The variables to be included in the imputation model are: concomitant disease of Baseline disease severity (PASI and sPGA), Baseline weight, treatment group, Concomitant PsA at baseline (Yes: Diagnosed or Suspected; versus: No), and measurements at each visit from randomization up to the end of the analysis period. For each endpoint, 20 'complete' datasets will be generated using SAS PROC MI. The imputed post-baseline measurements will be rounded to the same precision as the observed data before the determination of responder status (e.g., PASI90).
- Analysis of imputed data sets. A CMH test, stratified by stratification factors, will be used to analyze categorical endpoints in each imputed dataset.
- Synthesis of imputation and analysis results. SAS PROC MIANALYZE will be used to generate the final inferences of the risk difference between treatment groups.

Of note, subjects who discontinued due to AE of "worsening of disease under study" will be counted as non-responders in all subsequent visits in the NRI and MI analyses, and will have their last observation prior to discontinuation carried forward in the LOCF analyses. For Observations in RZB_75/RZB_75, and RZB_150/RZB_150 arms in Part B, LOCF is continued across Part A and Part B. LOCF will not carry forward from Period A to Period B for PBO/RZB_75, and PBO/RZB_150 arms.

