3.3.4 Removal of patients from therapy or assessments

3.3.4.1 Removal of individual patients

All patients have the right to withdraw from the study at any time without the need to justify their decision. The investigator has the right to remove patients from the study for noncompliance, administrative, or other reasons. It should be clearly understood that an excessive rate of withdrawals can render the study results uninterpretable. The sponsor reserves the right to remove any study patient from the trial for non-compliance.

An individual patient is to be withdrawn from trial treatment if:

- The patient withdraws consent for trial treatment or trial participation, without the need to justify the decision.
- The patient can no longer be treated with trial medication for other medical reasons (such as surgery, AEs, other diseases, or pregnancy)
- Development of a toxicity or AE which warrants BI 655066 discontinuation including but not limited to SAEs or suspected unexpected serious adverse reactions (SUSARs).
- If prohibited treatment is used during the study for any indication, the patient must discontinue use of the prohibited treatment if he/she wishes to continue in the study. In case of undue safety risk for the patient, the patient should discontinue study treatment at the discretion of the investigator. If the patient received a live virus vaccination during the study, the patient must discontinue study treatment.
- If the patient experiences an intolerable increase of psoriasis during the course of the trial the patient will be discontinued from the trial to receive rescue treatment as deemed appropriate by the investigator.
- The patient has repeatedly shown to be non-compliant with important trial procedures and, in the opinion of both, the investigator and CML, is not willing or able to stick to the trial requirements in the future.

Discontinuation of study medication should not lead to withdrawal from the study. If possible the patient should complete all study visits and procedures as initially planned.

Given the patient's agreement, the patient will undergo the procedures for early treatment discontinuation and follow-up as outlined in the [Flow Chart](#) and [Section 6.2.3](#). If a patient becomes pregnant, refer to [Section 5.3.6.2](#) for instructions.

Patients who discontinue the trial after receiving the first dose of study medication at Visit 2

will not be replaced.

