4.2.2 Restrictions

4.2.2.1 Restrictions regarding concomitant treatment

The medications (or classes of medications) listed in [Table 4.2.2.1: 1](#) must not be taken for the time periods as specified.

Table 4.2.2.1: 1 Restricted medications

Medication or class of medications	Restriction duration (through EOO Visit)
guselkumab , tildrakizumab	not allowed prior or during trial participation
briakinumab, ustekinumab (sterala [®]), secukinumab (Cosentyx [®])	6 months prior to randomisation
Brodalumab (Lumicef [®]), ixekizumab (Taltz [®])	4 months prior to randomisation
adalimumab (Humira [®]) , infliximab (Remicade [®]) investigational products for psoriasis (non-biologics)	12 weeks prior to randomisation
etanercept (Enbrel [®]) live virus vaccinations	6 weeks prior to randomisation
any investigational device or product (excludes psoriasis products) other systemic immunomodulating treatments (e.g., methotrexate, cyclosporine A, corticosteroids ¹ , cyclophosphamide, tofacitinib (Xeljanz [®]), apremilast) other systemic psoriasis treatments (e.g., retinoids, fumarates, any other drug known to possibly benefit psoriasis) photochemotherapy (e.g., PUVA)	30 days prior to randomisation
phototherapy (e.g., UVA, UVB) topical treatment for psoriasis or any other skin condition (e.g., corticosteroids ² , vitamin D analogues, vitamin A analogues, retinoids, salicylvaseline, salicylic acid, lactic acid, tacrolimus, tar, urea, α -hydroxy [fruit acids])	14 days prior to randomisation

¹ No restriction on corticosteroids with only a topical effect for non-skin indications (e.g., inhalative corticosteroids to treat asthma or corticosteroid drops used in the eye or ear).

² Exception: Topical steroids of medium such as Locoid or weak such as prednisolone for use on the face, axilla, and/or genitalia with a restriction of use within 24 hours prior to trial visit in which PASI is assessed.

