7.3.3 Further endpoint analyses

Change from baseline in PSS at Week 16 will be analysed by the van Elteren test between the BI 655066 arm and placebo arm. The other further endpoints will be summarised descriptively, with number and proportion of responders for dichotomous endpoints and mean, median, SD and IQR presented for continuous variables.

Time to onset of *Endpoint*, the time to event will be calculated as:

- Time to first onset (with observed event) = [date of first onset] – [date of first active treatment] + 1
- If a patient never attains *Endpoint* (e.g., PASI75 or PASI90), then that patient's time to first onset will be censored at the last visit where the *Endpoint* was measured (e.g., PASI).

Time to Loss of *Endpoint* (from time of randomisation), defined using the following algorithm:

- a) Never attains *Endpoint* (Failure at time 0)
- b) After achieving *Endpoint*, patient will be a failure if they subsequently do not achieve *Endpoint* and either discontinue from the study or switch therapy

while still not achieving *Endpoint*. Time to failure will be calculated using date of first failure to achieve *Endpoint*.

- c) Patients randomised to placebo will have Week 16 (i.e. when they begin taking BI 655066) as Day 0 for determining Time to Loss of response.
- d) Patients who maintain *Endpoint* throughout the study will be censored at their last measurement

Time to Loss of *Endpoint* (from time of achieving *Endpoint* or from specific point in time) will be defined as above but only for those patients that have achieved *Endpoint*.

All Time to Event endpoints will be presented using Kaplan-Meier curves.

As sensitivity analysis, the primary and secondary endpoints will be analysed in the same way based on PP Population.

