10.1.3 Analyses of Time-to-Event Variables

Time-to-event analysis will be done for RZB_75, RZB_150, PBO treatment arms for Part A, and all RZB_75/ RZB_75, RZB_150/ RZB_150 treatment arms for the entire study.

For the time to first achievement of Endpoint, the time to event will be calculated as:

- Time to first achievement (with observed event) = [date of first achievement] – [date of first study drug] + 1
- If a subject never attains an endpoint, then that subject's time to first achievement will be censored at the last visit where variable was measured. Censoring will be done within Part A for the analyses in Part A, and over the entire study for cross-period analyses. For example, if the first time a PASI 90 response is achieved in Part B, then PASI 90 will be censored for Part A analysis only.

Time to loss of response will be evaluated from the time of achievement of the same endpoint, and defined using the following algorithm:

- Never attains Endpoint (Failure at time 0)
- After achieving Endpoint, subjects will be considered loss of response if they subsequently lost the response or discontinue from the study due to AE of "Worsening of disease under study."
- Subjects will be censored at their last assessment if they do not lose the endpoint or discontinue from the study due to reasons other than AE of "Worsening of disease under study." Time to failure will be calculated starting from date of first achievement of the endpoint.

Time to event will be analyzed using Kaplan-Meier estimates for each treatment group. Treatments comparisons will be performed using stratified Log-rank test.

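### Patients who take prohibited psoriasis therapy and stay on study are scored on observed PASI and sPGA; Week 52 and Part B response rates need a rule (minor; primary result not at risk)

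*SAP*

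**What the plan says.** **Who may stay.** Protocol 3.3.4.1 deals with a patient who takes prohibited treatment for any indication: "the patient must discontinue use of the prohibited treatment if he/she wishes to continue in the study". Continued participation is therefore allowed. The same section asks that patients who stop study drug still attend all visits where possible.

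**How response is scored.** In SAP 10.1.4, non-responder imputation (NRI) is triggered by a missing value: "The NRI analysis will categorize any subject who has missing value at a specific visit as non-responder for that visit". The exception is a missing visit with response both before and after it, which counts as response. There is one event rule: patients who discontinue because of an adverse event of worsening of the disease under study "will be counted as non-responders in all subsequent visits in the NRI and MI analyses". Protocol 7.5 also covers missing data only.

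**What else touches prohibited therapy.** The per-protocol criteria listed in SAP 5.1 are share of injections received, at least one post-baseline PASI, and baseline severity. SAP 7.4 counts patients who received prohibited treatment, but this does not change their response status.

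**How long the protocol expects an effect to last.** Protocol Table 4.2.2.1: 1 sets the periods off therapy before randomisation. They are 14 days for phototherapy and for "topical treatment for psoriasis or any other skin condition", 30 days for other systemic agents, and longer for biologics, up to "6 months prior to randomisation" for ustekinumab and secukinumab. The topical restriction has a footnote: "Exception: Topical steroids of medium such as Locoid or weak such as prednisolone for use on the face, axilla, and/or genitalia".

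**The concern.** A patient who takes a prohibited psoriasis therapy, stops it and stays has no missing value and no discontinuation for worsening, so neither SAP rule applies. PASI and sPGA count as observed, even at a visit where the protocol's own wash-out would say the other therapy may still be acting. Improvement from that therapy can then be reported as response, or maintained response, to the randomised dose.

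This matters most after Week 16. The Week 52 endpoints and the Part B rates among patients responding at Part B entry (SAP 10.3 and 10.3.1) bear on the maintenance-of-response objective. They are descriptive, and every patient is on risankizumab by then, so no control arm would show the inflation. The SAP already treats discontinuation for worsening as failure; its silence on other psoriasis therapy leaves that logic incomplete.

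**Working it through.** **1. Does any rule catch the patient?**

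| Possible rule | Applies to a user who stays and attends? |
|---|---|
| NRI for a missing value (SAP 10.1.4) | No, the value is present |
| Worsening-AE discontinuation (SAP 10.1.4) | No, the patient has not discontinued |
| LOCF or multiple imputation (SAP 10.1.4) | No, nothing to impute |
| Listed per-protocol criteria (SAP 5.1) | No therapy criterion |
| Deviation table (SAP 7.4) | Counted only |

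**2. Does stopping the therapy settle it?** Part B PASI visits (Weeks 22, 28, 34, 40, 46, 52) are 6 weeks, or 42 days, apart. sPGA visits (Weeks 28, 40, 52) are 84 days apart. Wash-out divided by the PASI interval:
- phototherapy: 14/42 = 0.3
- other systemics: 30/42 = 0.7
- adalimumab, infliximab (12 weeks): 84/42 = 2.0
- ustekinumab, secukinumab (6 months, about 182 days): 182/42 = 4.3

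By the protocol's own standard, carry-over can reach one scored visit or several, depending on the agent.

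**3. Size after Week 16.** The inputs are 56 per risankizumab arm and 56 placebo patients split equally into two switch sequences of 28. One patient scored as responder instead of non-responder moves the rate by 1/n:
- 1/56 = 1.8 points; 1/28 = 3.6 points.
- Among PASI 90 responders at Part B entry, the planning rate of at least 65% gives 0.65 × 56 = 36.4. The denominator is then about 36 to 56 and the shift 1.8 to 2.8 points (1/56 to 1/36).

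For scale, compare with one 95% half-width, 1.96·√(p(1−p)/n). The Week 52 rate p is not given; 65% to 85% is assumed.

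| p | n | Half-width (points) | Patients to shift by one half-width |
|---|---|---|---|
| 65% | 56 | 12.5 | 7.0 |
| 85% | 56 | 9.4 | 5.2 |
| 65% | 28 | 17.7 | 4.9 |
| 85% | 28 | 13.2 | 3.7 |

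**4. Is the Week 16 primary result at risk?** First, the plan's own figure. With 65% vs 5%, two-sided 0.05 and 95% power, the two-proportion formula gives 14 per arm without continuity correction and 17 with it, which matches Protocol 7.7. For both comparisons, 0.95² = 90.25%, matching the stated overall power of at least 90%.

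At the actual 56 per arm, power = Φ[(Δ√n − 1.96·√(2p̄(1−p̄))) / √(p₁(1−p₁)+p₂(1−p₂))]. The share of users is assumed.

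| Scenario | Rates | Power per comparison |
|---|---|---|
| Planned | 65% vs 5% | >99.99% |
| 10% of active arm use, all of them responders set to failure | 55% vs 5% | >99.99% |
| 20%, same | 45% vs 5% | 99.95% |
| 30%, same | 35% vs 5% | 98.5% |
| No rule; 30% of placebo use, 65% of otherwise non-responding users respond | 65% vs 23.5% | 99.7% |

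For the last row, 0.05 + 0.30 × 0.95 × 0.65 = 0.235. In the 30% active-arm case, power for both doses is 0.985² = 97.0% if the comparisons are treated as independent.

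Tipping counts use the unstratified risk-difference test, starting from 36/56 vs 3/56. It takes 27 active responders reclassified as failures (9/56 vs 3/56, p = 0.063), or 23 extra placebo responders (36/56 vs 26/56, p = 0.053), before p exceeds 0.05.

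**The case against.** **Observed values are a legitimate choice.** Efficacy follows the intent-to-treat principle (Protocol 7.3), and keeping observed data in patients whom the protocol allows to continue is consistent with that. This stands as a defence of the present analysis. However, the SAP does not state it as its choice, and it takes the opposite line for worsening. Keeping the present result alongside meets the objection.

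**The extent will be visible, and the per-protocol criteria are still open.** Both are true. But the deviation and medication tables do not alter any rate, and the SAP's per-protocol analysis serves the primary endpoint, not Week 52.

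**A permanent failure rule would overcorrect.** This stands. One phototherapy course early in the trial, with a 14-day wash-out, should not make a patient a Week 52 failure. The rule has to be limited in time.

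**Consequence is hypothetical.** No usage rate is given and the exposed endpoints are descriptive. This stands, and it is why the point is minor.

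A reader might also infer two stronger claims that the documents do not support:
- *That rescued patients can stay and be scored as responders.* Protocol 2.3, 3.3.4.1 and 4.2.1 each say that a patient needing rescue is discontinued from the trial. Later visits are then missing and become non-response under NRI. The 3.3.4.1 list is headed as withdrawal from treatment rather than from the trial, but a rescued patient who stayed would be a departure from a rule stated three times.
- *That time to loss of response has the same gap*, because Protocol 7.3.3 mentions patients who "either discontinue from the study or switch therapy" and SAP 10.1.3 does not. The protocol counts a switch only in a patient who has already ceased to meet the endpoint, and dates failure at that first non-achievement. SAP 10.1.3 reads "subjects will be considered loss of response if they subsequently lost the response or discontinue from the study due to AE" of worsening, so any lost response already counts. Every switch failure under the protocol is therefore a loss under the SAP. Making therapy start a loss event would contradict the protocol on both trigger and date.

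**Conclusion.** The gap is real but minor. Under SAP 10.1.4, a patient who takes prohibited psoriasis therapy and stays on study is scored on observed PASI and sPGA, so carry-over benefit can count as response to the randomised arm. This mainly affects the descriptive Week 52 rates and the Part B rates among entry responders. Around 5 to 7 such patients of 56, or 4 to 5 of 28, would be needed to move a Week 52 rate by one half-width, if that rate lies between 65% and 85%.

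The Week 16 conclusion is safe under the planning rates, even with assumed use of 30%. The direction of any Week 16 effect is mixed: unrecognised benefit in placebo shrinks the difference, and benefit in an active arm enlarges it. It should not be described as simply conservative.

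**What to change.** Add one rule to SAP 10.1.4. A subject who starts a prohibited systemic, biologic or phototherapy that could improve psoriasis is a non-responder in the NRI and MI analyses at visits from that start until the therapy's Table 4.2.2.1: 1 wash-out has passed after it stops, or through end of study if it is not stopped. LOCF uses the last value before the start. The rule should take precedence over observed values and over the exception for a missing visit between two responses. Guselkumab and tildrakizumab have no finite period in the table, so the SAP should name one; end of study is the natural choice. Topicals do not trigger the rule.

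Classify the therapies blind and fix the list before the interim unblinding. Entries recorded later can be classified against it by BI staff, who stay blinded until final lock (SAP 4.4). Report the present observed-value result as a supplementary analysis.

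No change is needed to the time-to-loss definition, and no protocol amendment.

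Cost: one SAP rule, one extra table and a short blinded medication review. Concomitant therapies are already recorded in the eCRF (Protocol 4.2.1). The documents do not say that indication is collected, so this may need checking, as may stop dates. Response rates may come out slightly lower.

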7.5 HANDLING OF MISSING DATA

Every effort should be made to collect complete data at all visits.

The following rules will be used to impute for missing data:

- For all non-binary endpoints, LOCF (Last Observation Carried Forward) will be used to impute missing values
- For all binary endpoints (i.e., endpoints that are either 1 (patient responded) or 0 (patient did not respond)):
 - If no data after that visit, then impute as failure (No Response Imputation [NRI])

- If data at visits before and after, only impute as success if both visits are successes;
- else impute as failure

Missing items from the PROs will be handled according to the respective measure instructions (cf. [Appendix 10.3](#)). If there is no data for a particular visit, then it will be imputed following the same rules as described above.

Sensitivity analyses to assess the robustness of the hypothesis testing results will include:

- LOCF (for binary endpoints)
- Logistic regression
- MMRM (for continuous endpoints)
- Multiple imputation (for binary endpoints)

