7.6 RANDOMISATION

Patients will be randomised in blocks to double-blind treatment, stratified by concomitant disease of PsA at baseline (Yes versus No) and body weight (≤ 90 kg versus > 90 kg). Patients will be randomised to 4 sequences in a ratio of 1:1:2:2 within each level of stratification.

Sequence 1: Weeks 0-16: Placebo, Weeks 16-52: BI 655066 75 mg

Sequence 2: Weeks 0-16: Placebo, Weeks 16-52: BI 655066 150 mg

Sequence 3: Weeks 0-16: BI 655066 75 mg, Weeks 16-52: BI 655066 75 mg

Sequence 4: Weeks 0-16: BI 655066 150 mg, Weeks 16-52: BI 655066 150 mg

BI will arrange for the randomisation and the packaging and labelling of trial medication. The randomisation lists will be generated using a validated system, which involves a pseudo-random number generator so that the resulting treatment will be both reproducible and non-predictable. The block sizes will be documented in the CTR. Access to the codes will be controlled and documented.

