7.7 DETERMINATION OF SAMPLE SIZE

The study is powered to show a benefit of BI 655066 over placebo in terms of PASI 90 response at Week 16. Based on the outcome from the trial 1311.2, the PASI 90 response rate at Week 16 is assumed to be at least 65% in the BI 655066 arm. There is only minimal data available on placebo response in the BI 655066 program but the phase 3 results from ustekinumab and secukinumab indicate a response rate for PASI 90 of approximately 5% in the placebo arm. With 2-sided significance level 5%, based on these assumptions (65% vs 5% PASI 90 response rates), 17 patients in the BI 655066 arm and 17 in the placebo arm will provide 95% power for each comparison and an overall power of at least 90%.

For the Japanese submission, the safety data of at least 100 Japanese patients exposed to BI 655066 at the registered dose(s) for 1 year or more is necessary for long team safety assessment as a result of the PMDA consultation meeting in 2015. This study will enrol a total of 168 patients, with 56 patients in each of the two BI 655066 arms and 56 patients in the placebo arm. It is expected that at least 68 patients exposed to BI 655066 75 mg and 68

Proprietary confidential information © 2017 Boehringer Ingelheim International GmbH or one or more of its affiliated companies

patients exposed to BI 655066 150 mg will reach at least 1 year exposure to BI 655066 in this clinical trial or in the following extension study. Other global phase III trials where Japanese patients are to be enrolled will make up for the remaining safety data requirements.

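### The multiple-imputation sensitivity analysis for PASI 90 appears to draw raw PASI from a normal model, which would understate response among imputed active-arm patients

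*SAP*

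**What the plan says.** Protocol 7.5 lists four sensitivity analyses for missing data: LOCF for binary endpoints, logistic regression, MMRM for continuous endpoints, and "Multiple imputation (for binary endpoints").

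SAP 10.2 makes non-responder imputation (NRI) primary for PASI 90 at Week 16, with LOCF and MI as sensitivity analyses. SAP 10.1.4 describes the MI step:

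- The measurement behind each endpoint is imputed, in 20 datasets, with PROC MI.
- The model holds baseline PASI and sPGA, baseline weight, PsA, treatment group and the measurements at each visit of the analysis period.
- Responder status is derived last: "The imputed post-baseline measurements will be rounded to the same precision as the observed data before the determination of responder status".
- Each dataset is analysed with the stratified CMH method, and the risk differences are combined with PROC MIANALYZE.
- Patients who discontinue for an adverse event of worsening disease count as non-responders, whatever is imputed.

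The algorithm appears only in the fallback clause, which begins "If MI is not applicable due to the nature of our data (e.g., MCMC algorithm does not converge"). In that case logistic regression or MMRM replaces MI. No transformation, lower limit or by-group imputation is stated.

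**The concern.** PASI runs from 0 to 72 (Protocol Appendix 10.1) and entry requires at least 12 (Protocol 3.3.2). A PASI 90 responder with baseline 12 therefore has a score of 1.2 or less, and one with baseline 20 a score of 2.0 or less. If about 65% of active patients respond, most Week 16 scores lie in a narrow band above zero, with a tail of higher scores among the rest.

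A normal distribution cannot take that shape. The tail raises its mean and SD, so a symmetric draw puts a large share below zero and too large a share above the PASI 90 cut. Rounding corrects neither.

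At stake is what the MI analysis means. NRI is deliberately pessimistic and LOCF freezes an earlier visit. MI is the one of the three meant to show the result if data are missing at random. A model that pulls missing active patients toward about 50% response gives a biased answer to that question.

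**Working it through.** **1. The plan's own figure.** Protocol 7.7 assumes response rates of 65% on active drug and 5% on placebo. With equal groups, it says that "17 in the placebo arm will provide 95% power for each comparison and an overall power of at least 90" percent. Inputs: two-sided 5%, 95% power, difference 0.60, mean rate 0.35.

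- Uncorrected: n = (1.960·√(2·0.35·0.65) + 1.645·√(0.65·0.35 + 0.05·0.95))² / 0.60² = 13.3, so 14 per arm.
- Continuity-corrected: (13.26/4)·(1 + √(1 + 4/(13.26·0.60)))² = 16.4, so 17 per arm.

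The figure is reproduced. The trial plans "56 patients in each of the two BI 655066 arms and 56 patients in the placebo arm". The documents give no figure for the MI step, and no PASI mean, SD, visit correlation or missing rate. What follows rests on assumed distributions.

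**2. Hand check of the mechanism.** Work with the ratio of Week 16 to baseline PASI and ignore covariates. Assume it is lognormal on active drug with log-SD 1.0 and P(ratio ≤ 0.1) = 0.65.

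- Median = 0.1·exp(−0.385) = 0.068; mean = 0.068·exp(0.5) = 0.112; SD = 0.112·√(e − 1) = 0.147.
- Normal model for that arm alone: P(below 0) = Φ(−0.112/0.147) = 22%; P(≤ 0.1) = Φ((0.1 − 0.112)/0.147) = 47%. That is 18 points below 65%.
- One variance over two active groups and placebo (assumed placebo SD 0.30): SD = √((2·0.147² + 0.30²)/3) = 0.211. P(below 0) = 30%; P(≤ 0.1) = 48%, or 17 points low.
- The same pooled model with draws restricted to 0 or above: (0.477 − 0.297)/(1 − 0.297) = 26%, or 39 points low.

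Pooling raises the negative share but hardly moves the shortfall. A bare floor makes the shortfall much worse, because negative draws count as responders and offset part of the error.

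**3. Simulation with covariates and earlier visits.** 56 per group; data missing at random; last observed visit Week 4, 8 or 12; visit correlation 0.7; baseline mean 20 (SD 8) or 27 (SD 12); active log-SD 1.0 or 1.5; placebo ratio 0.95 (SD 0.30); values rounded to 0.1. The 65% case was run with 5% and 10% missing, the 75% case with 5%.

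| Imputation of Week 16 PASI | Negative, active | Imputed PASI 90 rate minus true rate |
|---|---|---|
| Raw, normal, arms pooled, true rate 65% | 33 to 35% | −14 to −20 points |
| Raw, normal, arms pooled, true rate 75% | 37 to 38% | −20 to −23 points |
| Raw, normal, by arm | 20 to 29% | −14 to −23 points |
| Raw, normal, pooled, minimum 0 | 0% | −40 to −51 points |
| log(PASI + 0.1), by arm | 0 to 2% | 0 to −3 points |

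The log model is favoured here because the data were generated as lognormal. A wider large-sample grid (correlation 0.5 to 0.9) gave 26 to 42% negative and 11 to 25 points low for the pooled model. The smallest values came at correlation 0.9. Other assumed distributions gave up to 44% negative, with shortfalls inside the same range. Predictive mean matching by group was within about 3 points of the true rate.

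**4. Effect on the risk difference (150 mg minus placebo).** Only imputed patients are affected. At 10% missing, 0.10·56 = 5.6 patients per group. A 14 to 20 point shortfall misclassifies about 0.8 to 1.1 of them, or 1.4 to 2.0 points of the group rate.

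| Missing | Pooled normal MI | NRI |
|---|---|---|
| 5% | −0.7 to −1.2 points | about −3 to −4 points |
| 10% | −1.4 to −2.1 points | about −6 to −7 points |

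**The case against.** The strongest reply is that the SAP never says the model is normal or that arms share a variance. It names PROC MI, lists treatment as a variable and mentions MCMC once, in an example. On that view the fault is missing detail. This stands in part: the normal model is an inference. It is a strong one, because PROC MI's MCMC assumes multivariate normality and rounding to the observed precision makes sense only for continuous draws. Matched donor values would need no rounding.

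The second reply is that the effect is negligible: about one patient per group at 10% missing, toward the null, against an assumed 60-point effect and with 56 per group where 17 suffice. This also stands, and it limits the point to the quality of a sensitivity analysis.

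A reader might infer more than the documents support:

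- That pooling the arms is the cause. By-arm normal models on raw PASI remain about 8 to 23 points low across the assumptions tried.
- That any exact percentage is a property of the plan. The sizes depend on distributions the documents do not give. At the plan's own 65%, the negative share at trial size is close to one third, not clearly above it.
- That LOCF and MI are the only sensitivity analyses of the primary endpoint. A per-protocol analysis is also planned (Protocol 7.3.3, SAP 10.2). They are the only two that vary the missing-data method.
- That logistic regression is available only if MCMC fails. Non-convergence is an example, so unsuitable data could also trigger the fallback. Still, a chain that converges to a badly fitting model would not clearly do so.

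**Conclusion.** The point holds in a limited form. On the natural reading of SAP 10.1.4, the MI analysis draws a bounded, skewed score from a normal model. Under plausible assumptions, roughly 26 to 44% of imputed active-arm Week 16 values would be negative and their PASI 90 rate about 11 to 25 points too low. The main cause is the normal draw on the raw score; pooling the arms mainly adds negative values.

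With 5 to 10% missing, also assumed, the MI risk difference is about 1 to 2 points too small. The error is conservative, smaller than the shift from NRI, and leaves the primary conclusion unchanged. It is worth correcting because MI is the only one of the three missing-data approaches that targets the missing-at-random result, and the correction is cheap.

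**What to change.** In SAP 10.1.4, name the method and scale:

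- Impute PASI at Weeks 4, 8, 12 and 16 by predictive mean matching (PROC MI, FCS REGPMM), with baseline PASI, sPGA, weight and PsA as predictors.
- Do this separately in the three Part A groups: 75 mg, 150 mg, and the two placebo sequences combined. Protocol 7.6 says "Patients will be randomised to 4 sequences in a ratio of 1:1:2:2 within each level of stratification", so imputing by sequence would split placebo into two sets of about 28.
- Then derive PASI 90, keep the non-response rule for discontinuation due to worsening, and pool the stratified risk difference as planned.
- Do not simply add a minimum of 0 to the present model.

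The cost is a few lines of SAP text and code. The downside is that donors come from at most about 56 patients per group. By-arm imputation on a log scale is a workable alternative, but it depends more on the distributional form.
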